8.1.5 Overall Survival (OS)

OS is defined as the time from first dose of study drug to the date of death due to any cause. OS (in months) is calculated as (date of death – date of first dose of study drug +1)/30.4. For patients who are continuing study at the time of an analysis, lost to follow-up or who withdraw consent, the OS endpoint will be censored on the last date that patients were known to be alive. The date last known to be alive is derived from the CRF and may include the latest Visit date for patients on-going study or the latest Date of Contact on the Long-Term Follow-Up/Survival Status page, whichever occurs latest. For patients with no follow-up after first dose of study drug, OS will be censored at the date of first dose.

8.1.6 Progression-Free Survival (PFS)

PFS is defined as the time from the first dose of study drug to the date of PD or death due to any cause, whichever occurs first. PFS (in months) will be calculated as (first event date – first dose date +1)/30.4.

Censoring rules will be applied to PFS:

Sponsor: Mirati Therapeutics, Inc.

Protocol no: 0103-020

- Patients lacking evaluation of disease after first study treatment will have their PFS time censored on the date of first dose with duration of 1 day unless they die within 2 tumor assessments of baseline, then they will be treated as an event with date of death as the event date.
- Patients with baseline or post-baseline assessments inadequate to apply RECIST criteria will have their event time censored on the date of the first dose of study drug.
- Event time will be censored on the date of the last evaluable assessment documenting absence of PD for:
 - Patients on-study and progression-free at the time of an analysis;
 - Patients who have PD or death on study after ≥ 2 consecutive missed tumor assessments (i.e., >12 weeks + 14 days after the last on-study disease assessment);
 - Patients given alternative cancer treatment prior to PD or death on-study.
- Patients who die on-study after ≥ 2 consecutive missed tumor assessments (i.e., >12 weeks + 14 days after the last on-study disease assessment) will have their event time censored on the date of the last evaluable assessment documenting absence of PD.

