- 11 Blood Samples for Biomarker Studies: Blood samples for biomarker studies will not be collected on subjects in the Phase 1 50 mg cohort, but will be required for subjects in all other cohorts. At the beginning of the study, sampling will be scheduled on Cycle 1 Day 15. During the study, emerging data may indicate that quality of information gained from the assessment should improve with increased duration of combination treatment. If so, the sample may be moved to Cycle 2 Day 1 and communicated to Investigators by Administrative Letter. Markers of interest in circulation include circulating PD-L1, Tregs, MDSCs, NK-cells, flow cytometry for T- and B-cell including CD4, CD8 and Ki67, and selected cytokines including CD8A, GZMB, IFN $\gamma$ , CXCL9, CXCL10, CXCL11, and TBX21.
- 12 ECGs: Single 12-lead ECGs are to be performed at screening and at points not accompanied by PK sampling, with the exception of C3D1, C4D1 and C7D1. On days when PK samples are being collected, the single ECG should be performed prior to the blood draw. Triplicate ECGs are to be performed to as noted in [Table 2](#). Assessments will include an evaluation of rhythm, heart rate, and PR, QRS, QT, and QTc intervals (Fridericia's formula). Respiration rate should be recorded during each ECG assessment.
- 13 Disease Evaluations: To be performed at screening (28 day window allowed) and every 8 weeks ( $\pm$  10 days window) from C1D1 for all other assessments except screening until Week 49 (~1 year) and then every 12 weeks. At screening/baseline, assessments are to include CT with contrast of the chest, abdomen and pelvis, as well as brain Magnetic Resonance Imaging (MRI) with and without gadolinium or Computed Tomography Scan (CT) with contrast, a whole body bone scan and evaluation of any superficial lesions. Subsequent disease assessments should include all sites of disease identified at baseline or suspected to have developed; bone scans may be performed at one-half the frequency of other radiology evaluations and should be performed during assessment for confirmation of disease response. For those sites that routinely use PET scans for assessment of bone lesions in lieu of skeletal scintigraphy, PET scans may be used on-study, with the same modality planned throughout the study for any given patient. More detailed guidance on exceptional circumstances is provided in the protocol.

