#### **9.4.4 Progression Free Survival**

Progression-free survival (PFS) is defined as the time from date of first study treatment to first PD or death due to any cause in the absence of documented PD. Censoring for the PFS endpoint will be assigned on the date of the last tumor assessment if no assessment of tumor progression is identified and the patient does not die while on study. For patients in whom two or more sequential assessments are missed, followed by the finding of tumor progression, the PFS endpoint will be censored on the date of the last tumor assessment before the gap. Patients lacking an evaluation of disease after first study treatment will have their PFS time censored on the date of first dose with duration of 1 day. Patients who start a new anti-cancer therapy prior to documented PD will have the endpoint censored at the date of the last tumor assessment prior to the start of the new therapy. The Kaplan-Meier method will be used to obtain the estimate of median progression-free survival time.

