### **Tumor Assessments**

All sites of disease must be assessed at baseline. Baseline assessments should be done as close as possible prior to study start. All required scans must be done within the window of time specified in the Schedule of Assessments (Table 1) prior to treatment. If the baseline assessment is inadequate, subsequent statuses generally should be indeterminate.

The determination of whether lesions are measurable is performed only at baseline. “Measurable” at baseline means eligible for selection as target lesions, and thus for quantitative assessment throughout the trial. Once selected as a target lesion, a lesion remains target throughout the trial.

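### SAP 8.1.6 censors patients whose only tumour assessments are inadequate at first dose, with no exception for death, which can bias PFS upward in a narrow group

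*SAP*

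**What the plan says.** SAP 8.1.6 opens with the event definition: "PFS is defined as the time from the first dose of study drug to the date of PD or death due to any cause". A list of censoring rules follows.

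- **First rule (no disease evaluation after first treatment).** The patient is censored at first dose and given a one-day duration, with this exception: "unless they die within 2 tumor assessments of baseline, then they will be treated as an event with date of death as the event date".
- **Second rule (assessments not good enough for RECIST).** "Patients with baseline or post-baseline assessments inadequate to apply RECIST criteria will have their event time censored on the date of the first dose". Nothing is said about death, and there is no time limit.
- **Remaining rules.** Censoring is at the last evaluable assessment for patients who are progression-free at the analysis, who start other cancer treatment, or whose PD or death follows two or more consecutive missed assessments.

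Protocol 9.4.4 also counts "first PD or death due to any cause in the absence of documented PD" as the event. It has no rule for inadequate assessments. Its general rule censors only when no progression is found and the patient does not die on study. Its sentence on unevaluated patients carries no death exception: "Patients lacking an evaluation of disease after first study treatment will have their PFS time censored on the date of first dose with duration of" (the time assigned is a single day).

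SAP 12.5.2 analyses PFS in the mITT population, so a patient who received both drugs stays in the analysis even if never evaluable for response.

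**The concern.** The two adjacent SAP rules treat similar patients in opposite ways. A patient with no scan who dies early is an event on the date of death. A patient with a scan that could not be read, who dies in the same interval, is removed on day 1. The documents give no reason for the difference, and the second rule departs from the event definition a few lines above it.

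The situation can arise in this trial. Protocol Appendix 5 calls a status indeterminate when target lesions are missed, cannot be measured accurately, or are imaged by an inconsistent method. On a poor baseline it says "If the baseline assessment is inadequate, subsequent statuses generally should be indeterminate". If deaths among such patients come early, dropping them at time zero removes early events and raises the Kaplan-Meier curve.

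The SAP also does not say which rule governs a patient who meets both, for example one with an inadequate baseline, no later scan and an early death.

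**Working it through.** **No plan figure to reproduce.** The documents state no event count, power or assumed median for PFS. The check is therefore a comparison of the rules, a timing check and an illustration.

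**1. The rules side by side (SAP 8.1.6)**

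| Patient who dies without documented PD or other cancer treatment | Rule | Result |
|---|---|---|
| No post-treatment evaluation, death within 2 assessments | First | Event at death |
| Scans done but none usable, death in the same interval | Second | Censored at first dose |
| Usable scan, death before two consecutive assessments are missed | None | Event at death |
| Usable scan, death after two or more missed assessments | Later rules | Censored at last evaluable assessment |
| Inadequate baseline, no later scan, early death | First and second | Not stated |

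The second row is the outlier among the early deaths.

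**2. When the second rule can matter.** PFS runs from first dose, which is Lead-in Day 1. Cycle 1 Day 1 follows the 7-day lead-in, so it is day 8. Scans are "every 8 weeks ( $\pm$ 10 days window) from C1D1".

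- First scheduled scan: 8 + 56 = day 64, with a window of day 54 to day 74.
- Two assessment intervals: 2 × 8 = 16 weeks, or 112 days.
- Month 2 in the SAP's units: 2 × 30.4 = 60.8, about day 61.

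A death at month 2 therefore usually precedes the first scan and is an event under the first rule. The gap concerns mainly deaths that follow an unreadable first scan at about week 8 to 9, plus patients with an inadequate baseline.

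**3. Illustration with assumed counts.** Take 17 patients. Two have only unusable scans and die within 3 months (3 × 30.4 = 91 days, so a death after a day-64 scan fits). Eight of the other 15 have events by 3 months, and there is no other censoring.

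- Deaths counted: (17 − 2 − 8)/17 = 7/17 = 41.2%.
- As written: the two leave at 1 day, 1/30.4 = 0.03 months, before any event; (15 − 8)/15 = 7/15 = 46.7%.
- Difference: 5.5 percentage points.

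**4. Effect on the median, by simulation.** Assumptions: exponential PFS with median 3.7 months (a figure protocol 1.1.1 reports for a different agent); k affected patients dying uniformly between about week 1 and week 16; no other censoring; 400 runs per setting. Entries are the typical Kaplan-Meier median in months.

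| N | k | Deaths as events | Censored at day 1 |
|---|---|---|---|
| 17 | 1 | 3.44 | 3.50 |
| 17 | 2 | 3.17 | 3.70 |
| 17 | 3 | 3.05 | 3.41 |
| 100 | 3 | 3.46 | 3.64 |
| 100 | 6 | 3.35 | 3.76 |
| 100 | 12 | 3.17 | 3.75 |

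The shift is about 0.1 to 0.5 months for 1 to 3 such deaths among 17, and about 0.2 to 0.6 months for 3 to 12 among 100. With k = 0 there is none. The simulated deaths start at week 1, earlier than a death after an unreadable on-study scan could normally occur, so these figures show direction and rough scale only.

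**The case against.** A reader might infer that early deaths in general become day-1 censorings and that PFS is therefore overstated. The documents do not support that. The first rule says that unevaluated patients are censored "unless they die within 2 tumor assessments of baseline", so deaths before a first scan, which are the main early-death group, remain events.

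The remaining group is narrow. The patient must have had a scan, the scan must have been unusable, no PD may have been documented, and there must be no adequate assessment. Under Appendix 5 a new lesion or non-target progression gives PD whatever the state of the target lesions, so rapid decline will often appear as PD or as no scan at all. Nothing in the documents shows that decline makes inadequate scans more likely. Phase 2 entry requires measurable disease and full baseline imaging, which limits inadequate baselines, though not inadequate later scans.

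The second rule could also be called a deliberate exception to the definition, since later rules censor some deaths too. One might further read a patient with only a not-evaluable scan as lacking evaluation, which would bring in the first rule. Both readings are possible, but neither is written down. The later rules differ in that they censor a death only after a gap in assessment.

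The illustration uses chosen counts, and SAP 12.5.2 plans medians, quartiles and plots, not a 3-month rate. The 5.5-point shift also lies well inside the exact 95% interval for 7/17, roughly 18% to 67%. These limits on size stand. They do not remove the inconsistency between the two rules.

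**Conclusion.** The point holds in a limited form. As written, the second rule in SAP 8.1.6 turns certain deaths into day-1 censorings: those in patients with no usable assessment, occurring at a time when the first rule would count the death. The possible bias is upward.

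Its size is unknown. The documents give no count of affected patients; it may be small or zero, and with none there is no bias. The 41.2% to 46.7% shift and the simulated medians are illustrations and rest on the stated assumptions. I take the second rule to mean patients with no adequate assessment at all, not those with one poor scan among good ones.

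The stakes are modest. PFS is secondary, summarised descriptively and not tested. Stage and expansion decisions use ORR. OS under SAP 8.1.5 keeps every death, so an early-death signal would still be visible there. The change is nonetheless worth making, because this is a stated rule that gives the wrong result if programmed literally, and not merely a missing detail.

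**What to change.** 1. In the second censoring rule of SAP 8.1.6, add the first rule's exception with the same anchor: "unless they die within 2 tumor assessments of baseline, then they will be treated as an event with date of death as the event date".
2. State that this death exception takes precedence when a patient meets both the first and the second rule.
3. Add the same exception to the no-evaluation sentence in protocol 9.4.4, so that the protocol and the SAP agree.

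The cost is one SAP clause and a sentence on precedence, plus one sentence in the protocol at its next amendment. SAP 4.0 provides for a final version before database lock, so the SAP change can be made there. No new data collection is needed.

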## 7.2 Efficacy

All patients enrolled in the study are to be evaluated for disease activity as outlined in the Schedule of Assessments (Table 1). Screening/baseline tumor assessments should include CT or MRI of the chest, abdomen, and pelvis, whole body bone scan, MRI of the brain and evaluation of any superficial lesions. On-study assessments will include all known and suspected sites of disease and will be performed at 8 week intervals until approximately 1-year and then every 12 weeks. The allowable windows for assessments are 4 weeks prior to first study treatment for screening/baseline assessments and  $\pm 10$  days for on-study disease assessments.

CT scans should be performed with contrast agents unless contraindicated for medical reasons. If intravenous contrast is medically contraindicated, the imaging modality to be used (either CT without contrast or MRI) should be the modality which best evaluates the disease, and the choice should be determined by the investigator in conjunction with the local radiologist. Depending on the adequacy for evaluation of disease, a combination of CT without contrast and MRI should most often be used. CT without contrast is preferred for evaluation of lesions in lung parenchyma. MRI is not adequate for evaluation of lung parenchyma but should also be performed to evaluate all other aspects of the chest. MRI of the abdomen and pelvis should substitute for CT with contrast unless the method does not adequately depict the individual's disease, in which case CT without contrast is preferred. For those sites that routinely use PET scans for assessment of bone lesions in lieu of skeletal scintigraphy, PET scans may be used on-study, with the same modality planned throughout the study for any given patient.

For patients having effusions or ascites, cytological proof of malignancy should be obtained prior to selection of the effusion as a non-target lesion. Effusions that have not been evaluated using cytology or were found to be non-malignant should not be considered to be cancer lesions.

Disease response will be assessed in accordance with RECIST 1.1 (Eisenhauer-2009). Appendix 5 provides guidance in using the response criteria and include a modification to RECIST 1.1 to address potential temporary treatment effects such as tumor lesion cavitation or flare response. Assessments will be performed until objective disease progression is documented by the investigator, or subsequent anti-cancer therapy is begun.

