## 9.2 Data Handling

Listings of all patient data will be prepared. Data summaries will be presented in tabular and/or graphical format and summarized descriptively, where appropriate. Details of planned analyses will be described in the [SAP](#).

For all variables, only the observed data from patients will be used in the statistical analyses; there is no plan to estimate missing data. Patients without a valid clinical response assessment will be assigned a best overall response of not evaluable (NE). Data from patients who are lost to follow-up or have missing observations before reaching an endpoint in any of the time-to-event analyses will be treated as censored with specific rules defined in the SAP.

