13 Disease Evaluations: To be performed at screening (28 day window allowed) and every 8 weeks (\pm 10 days window) from C1D1 for all other assessments except screening until Week 49 (~1 year) and then every 12 weeks. At screening/baseline, assessments are to include CT with contrast of the chest, abdomen and pelvis, as well as brain Magnetic Resonance Imaging (MRI) with and without gadolinium or Computed Tomography Scan (CT) with contrast, a whole body bone scan and evaluation of any superficial lesions. Subsequent disease assessments should include all sites of disease identified at baseline or suspected to have developed; bone scans may be performed at one-half the frequency of other radiology evaluations and should be performed during assessment for confirmation of disease response. For those sites that routinely use PET scans for assessment of bone lesions in lieu of skeletal scintigraphy, PET scans may be used on-study, with the same modality planned throughout the study for any given patient. More detailed guidance on exceptional circumstances is provided in the protocol.

Sponsor: Mirati Therapeutics, Inc.

Protocol no: 0103-020

- 14 Adverse Events: SAEs will be reported from the time of informed consent until 90 days after the last administration of mocetinostat or durvalumab. Adverse events will be reported from the first day of study treatment until at least 28 days after last dose of study drug, and until resolution or stabilization of acute AEs and/or ongoing SAEs. After the 90-day SAE observation period, post-treatment follow-up may be performed by remote contact (e.g., telephone call).
- 15 End of Treatment: Assessments that have been completed in the previous 4 weeks do not need to be repeated (8 or 12 weeks for tumor assessments in accordance with schedule).
- 16 Long Term Follow-up: Blood samples for MEDI4736 PK and ADA will be collected approximately 90 days after the last infusion of durvalumab. Survival status and subsequent therapies will be collected during long term follow-up every 2 months (± 14 days) from the date the subject was discontinued from study treatment until death or lost to follow-up. Follow-up beyond 90 days after last treatment may be performed by telephone contact.

Sponsor: Mirati Therapeutics, Inc.

Protocol no: 0103-020

Table 2: Schedule of Triplicate ECGs, PK and ADA Assessments

Nominal Cycle Day	Mocetinostat ¹		Durvalumab ^{1,2}	
	Triplicate ECG ³	PK Sample ^{5,6,7}	PK Sample ^{5,6}	ADA Sample ⁶

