12.5.2 Time-to-event Variables

Time-to-event variables, DR, PFS, and OS, will be summarized by phase and by dose level/cohort and overall within each phase, descriptively using the Kaplan-Meier estimate (SAS® PROC LIFETEST). The median, 25th percentile, and 75th percentile of DR, PFS, and OS and their two sided 95% CIs using the complementary log-log transformation method ([Collett, 1994](#)) will be calculated where appropriate. In addition, minimum and maximum will also be displayed. Kaplan-Meier plots will be provided for DR, PFS, and OS.

Sponsor: Mirati Therapeutics, Inc.

Protocol no: 0103-020

DR, PFS, and CBR will be based on the Response Assessments by the Investigator. DR will be conducted in both the clinical activity evaluable and mITT populations. PFS and OS will be conducted in the mITT population.

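### The SAP equates two missed scans with more than 98 days, which does not fit the 8- and 12-weekly scan schedule; if the number is programmed, PFS and DR events after a single missed scan are censored

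*SAP*

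**What the plan says.** SAP 8.1.4 (DR) and 8.1.6 (PFS) each contain two bullets that censor at the last evaluable assessment when progression or death follows two or more "consecutive missed tumor assessments (i.e., >12 weeks + 14 days after the last on-study disease assessment". The limit is introduced as a restatement of the words, and it does not vary with study phase. The first bullet of 8.1.6 uses a count without a day limit: patients with no disease evaluation after first treatment are censored at first dose "unless they die within 2 tumor assessments of baseline".

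The schedule is the same in both documents. SAP Table 1, footnote 13, sets disease evaluations every 8 weeks, with a 10-day window either side, "from C1D1 for all other assessments except screening until Week 49 (~1 year) and then every 12 weeks". Protocol 7.2 says that on-study assessments "will be performed at 8 week intervals until approximately 1-year and then every 12 weeks".

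Protocol 9.4.4 also counts scans and gives no day limit: "For patients in whom two or more sequential assessments are missed, followed by the finding of tumor progression, the PFS endpoint will be censored". Protocol 9.4.3 has no missed-scan rule for DR. Protocol 9.2 says that incomplete time-to-event data "will be treated as censored with specific rules defined in the SAP". The planned outputs in SAP 12.5.2 include "The median, 25th percentile, and 75th percentile of DR, PFS, and OS and their two sided 95% CIs", with Kaplan-Meier plots.

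**The concern.** The count and the day limit are presented as one rule, but under this trial's schedule they classify the same patient differently. A day limit is easy to code, while the SAP never defines a missed assessment, so a programmer could well code the number. Two programmers could then produce different PFS and DR results from the same text.

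Under the number, censoring depends on the outcome. After a long gap, a patient whose next scan shows progression is moved back and censored at the scan before the gap. A patient whose next scan is clean stays in follow-up. This is informative censoring of two secondary endpoints, which the optional expansions of Cohorts 3 and 4 to 100 patients are partly meant to characterise (SAP 6.2).

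**Working it through.** **1. The SAP's limit.** 12 × 7 + 14 = 98 days. With the same 14-day allowance, two 6-week intervals give 2 × 42 + 14 = 98. Neither document has a 6-weekly schedule.

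**2. Two intervals on the actual schedule.**
- 8-weekly: 2 × 56 = 112 days; the second window closes at 112 + 10 = 122.
- Last scan at Week 41 (next due Weeks 49 and 61): 56 + 84 = 140 days; closes at 150.
- 12-weekly: 2 × 84 = 168 days; closes at 178.

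**3. Gaps between scans.** Gap = nominal gap + (d2 − d1), where each deviation d runs from −10 to +10 days, giving 21 × 21 = 441 combinations.

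| Situation | Gap (days) | Over 98 days |
|---|---|---|
| 8-weekly, none missed | 36-76 | 0/441 |
| 8-weekly, one missed | 92-132 | 413/441 (94%) |
| Week 49 missed, Week 41 to 61 | 120-160 | 441/441 |
| 12-weekly, none missed | 64-104 | 21/441 (4.8%) |
| 12-weekly, one missed | 148-188 | 441/441 |

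Row 2: 112 + (d2 − d1) ≤ 98 needs a difference of −14 or less, which is 1 + 2 + … + 7 = 28 combinations, and 441 − 28 = 413. Row 4: 84 + (d2 − d1) > 98 needs +15 or more, which is 6 + 5 + … + 1 = 21. In that row no scan has been missed.

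**4. Deaths after an on-time scan.** A death is censored with only one scan window closed on days 99-122 (8-weekly), 99-150 (last scan Week 41) or 99-178 (12-weekly). In the 8-weekly phase the first window closes on day 56 + 10 = 66, so deaths on days 67-98 follow one closed window and remain events.

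**5. Size, by simulation.** The documents give no missed-scan rate, so 5, 10 and 20% are assumed. Median PFS of 3.7 months and median DR of 12.5 months are borrowed from the Phase 1 pembrolizumab study in Protocol 1.1.1. Other assumptions are exponential times, independent missed scans, uniform window deviations, deaths as 0-30% of PFS events or 0-15% of DR events, and 24-48 months of follow-up. Unless stated, the 98-day limit applies only after an on-study scan.

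| Scans missed | 5% | 10% | 20% |
|---|---|---|---|
| 12-month PFS, no deaths: count → 98-day (%) | 12.3 → 12.9 | 12.8 → 14.1 | 13.8 → 16.6 |
| Rise across settings (points) | 0.4-0.6 | 0.9-1.3 | 1.8-2.9 |
| Rise if the limit also runs from C1D1 (points) | 0.8 | 1.7 | 3.7 |
| Largest fall in PFS curve, about days 65-180 (points) | 0.8 | 1.5 | 2.5 |
| Median PFS, 15% deaths: count → 98-day (months) | 4.21 → 4.18 | 4.21 → 4.18 | 4.74 → 4.21 |
| 18-month DR, no deaths: count → 98-day (%) | 40.6 → 43.8 | 41.1 → 46.4 | 43.5 → 52.8 |
| Rise across settings (points) | 2.8-3.2 | 4.7-5.4 | 8.0-9.5 |
| Median DR, no deaths: count → 98-day (months) | 14.5 → 15.2 | 14.7 → 15.9 | 15.3 → 19.9 |

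The early fall in PFS arises because a patient moved back to an earlier censoring date leaves the risk set, so events in between weigh more. Later the missing event dominates and the curve rises.

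**6. Sampling error for scale.** SE = √(p(1 − p)/n).
- 12-month PFS, p = 0.128: 8.1 points at n = 17 and 3.3 at n = 100.
- 18-month DR, p = 0.411: 9.0 points with 30 responders (30% of 100), 10.5 with 22 (50% of 44) and about 22 with 5 (30% of 17).

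**The case against.** The strongest reply is that the error is conditional. The words in the SAP match Protocol 9.4.4, the SAP is to be read together with the protocol, and a programmer who counts missed scans makes no error. PFS and DR are secondary and descriptive. This stands and limits the severity. It does not remove the conflict: Protocol 9.2 hands the censoring rules to the SAP, and the SAP states two that disagree.

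Three stronger readings are tempting and do not hold:

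- **The bias is always upward.** For DR the curve is raised almost throughout. For PFS it is raised late but lowered between about days 65 and 180, by a similar amount. Median PFS, a planned output, is unchanged or lower when the limit applies after an on-study scan. If the limit also runs from C1D1, one simulation gave higher medians (4.47 → 4.75, 4.86 → 5.20 and 5.23 → 5.39 months). The SAP's text favours the first reading, since its limit runs from the last on-study assessment and Protocol 7.2 treats baseline assessments separately. No single direction can be claimed for median PFS.
- **Every death after one missed scan is censored.** Only deaths in the day ranges of step 4 are affected.
- **The DR rule contradicts the protocol.** Protocol 9.4.3 has no missed-scan rule, so for DR the conflict is only between the SAP's own words and number.

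The simulated sizes also rest on assumed missed-scan rates and on medians from another drug's study. They show direction and order of magnitude and are not forecasts.

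**Conclusion.** The inconsistency is confirmed by calendar arithmetic alone: 98 days does not represent two missed scans at any point in this schedule. If the number is programmed, nearly all progressions found after one missed 8-weekly scan, and all of those found after one missed scan later on, are censored. For PFS this is contrary to Protocol 9.4.4. In the 12-weekly phase a few fully compliant gaps are censored too.

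The effect on estimates is modest for PFS and larger for DR. At 5-10% missed scans, median DR rose by about 0.2-2.4 months across settings, and at 20% by about 3-5 months; the spread comes from the scan grid and the assumptions. On the planned Kaplan-Meier plots the bias is below or near sampling error even in a 100-patient cohort. ORR, the stage rules and their error rates are untouched. This should be fixed because it is wrong as written and cheap to correct; it does not threaten the primary analysis.

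**What to change.** In SAP2, delete the parenthesis with the day limit from all four bullets of 8.1.4 and 8.1.6, and add a definition along these lines:

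- Assessments are scheduled 8-weekly from C1D1 up to Week 49 and 12-weekly after that, each with a ±10-day window.
- Each scan is assigned to the nearest scheduled week, with ties going to the earlier week.
- A scheduled assessment counts as missed for a given progression or death if no scan is assigned to it and its window closed before that event.
- If no evaluable post-baseline scan precedes the progression or death, counting starts at C1D1. If two or more assessments were missed, PFS is censored at the date of first dose with a duration of 1 day.

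The last item agrees with the first PFS bullet and covers a case the SAP leaves open: a first post-baseline scan that shows progression after two missed scans.

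The cost is a few lines of SAP text and one programming rule. SAP 4.0 already plans SAP2 before database lock, and no protocol amendment is needed because Protocol 9.2 leaves the censoring rules to the SAP. Late PFS and DR estimates may come out slightly lower than under the 98-day limit.
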